2.0	
 Document updated throughout to align with the removal of Cohort A (Moderate Symptomatic AS) in protocol revision D Updated Kaplan-Meier standard error to use Greenwood’s method Remove required summary of domain scores for the efficacy endpoint change in KCCQ Removal of “Additional details have been detailed in the SAP for the planned subgroup analyses (Section 7.9.4) including identification of the endpoints to be analyzed as well as the addition of subgroup analysis based on NT-proBNP which was identified as clinically important” from Section 7.11 as the details in this document align with the subgroup analyses as specified in CIP revision D Added Section 9 (References) 	[name], Principal Statistician

2. List of Abbreviations and Definitions of Terms

Abbreviation	Definition
AE	Adverse event
AS	Aortic stenosis
BMI	Body mass index
BSA	Body surface area
BVD	Bioprosthetic valve dysfunction
BVF	Bioprosthetic valve failure
CEC	Clinical Events Committee
CIP	Clinical Investigation Plan
CRF	Case Report Form
DCS	Delivery catheter system
DVI	Doppler velocity index
E	Early diastolic mitral inflow velocity
e’	E prime; mitral annular early diastolic velocity

Abbreviation	Definition
E:e'	Ratio of early (E) mitral inflow velocity to early (e') mitral annular velocity
EOA	Effective orifice area index
EOAI	Effective orifice area index
GLS	Global longitudinal strain
KCCQ	Kansas City Cardiomyopathy Quality of Life
LVEF	Left ventricular ejection fraction
LVOT	Left ventricular outflow tract
NT-proBNP	N-terminal pro B-type natriuretic peptide
NYHA	New York Heart Association
PPM	Patient-prosthesis mismatch
PPI	Permanent pacemaker implant
QoL	Quality of Life
SAE	Serious adverse event
SAP	Statistical Analysis Plan
SVI	Stroke volume index
TAV	Transcatheter aortic valve
TAVR	Transcatheter aortic valve replacement
TEE	Transesophageal echocardiography
VARC-2	Valve Academic Research Consortium
VTI	Velocity time integral
6MWT	Six-minute walk test

3. Introduction

This Statistical Analysis Plan (SAP) has been designed to document, before data are analyzed, the rationale for the study design, and the planned analyses that will be included in study reports and study-specific publications for the Evolut™ EXPAND TAVR I Feasibility Study. This version of the analysis plan was developed under the approved Clinical Investigation Plan (CIP) and approved Case Report Form (CRF) Requirements.

4. Study Objectives

The primary objectives of this feasibility study are as follows:

1. Characterize the spectrum of cardiac function, symptomology, and severity of aortic stenosis in the study populations,
2. Estimate event rates for potential safety and effectiveness endpoints to be evaluated in pivotal studies for the proposed patient populations, and
3. Evaluate the effect of TAVR on cardiac function, functional capacity, effort tolerance, and patient-reported quality of life in the study populations.

The study objectives and associated endpoints are intended to fully characterize the spectrum of aortic stenosis (AS) severity, left ventricular (LV) function, and symptomology of patients with moderate

symptomatic and severe asymptomatic AS, provide information on event rates for pivotal sample size estimations, and refine the entrance criteria for future pivotal studies. The full list of protocol defined endpoints are detailed in Section 7.9. Of the protocol defined endpoints, the following key study endpoints have been identified:

Key Safety Endpoints:

- All-cause mortality at 30 days and 6 months
- All stroke (disabling and non-disabling) at 30 days and 6 months
- Valve-related dysfunction requiring repeat procedure at 30 days and 6 months
- New permanent pacemaker implant (PPI) at 30 days and 6 months

Key Efficacy Endpoints:

- Cardiovascular and heart failure hospitalizations at 30 days and 6 months
- Heart failure events at 30 days and 6 months
- Change in Kansas City Cardiomyopathy Questionnaire (KCCQ) at 6 months
- Change in Six-Minute Walk Test (6MWT) at 6 months
- Change in cardiac function by echo (LVEF, Peak GLS, E:e') at 6 months

5. Investigation Plan

5.1 Study Design

This is a prospective, descriptive, interventional, multi-center, single-arm, pre-market, feasibility study. The study will involve up to 75 subjects with severe, asymptomatic AS implanted using the Medtronic Evolut PRO+ TAVR system among up to 25 centers in the United States, Canada, Europe, Israel, Australia, and New Zealand. As not all patients consented for evaluation will go forward to implantation, the number of subjects consented for the study is expected to be higher than 75 (up to 150). No site will implant more than 15 total subjects without prior authorization from Medtronic in order to minimize bias.

5.2 Purpose

The purpose of this study is to obtain initial procedural safety and efficacy data on the use of the Medtronic self-expanding Evolut PRO+ TAVR system in patients with severe, asymptomatic AS. Data will be used to inform the design of pivotal studies to support expansion of the current indication to include these patient populations.

5.3 Follow-up and Study Duration

Subjects will be consented for follow-up through five years following implantation, and all implanted subjects will be followed per protocol through five years following implantation. Subject follow-up visits post-implantation will occur at discharge, 30 days, 6 months, and annually through five years. Subjects who exit from the study after implantation will not be replaced. The enrollment period is estimated to be between 9 and 20 months, and the estimated total study duration (first subject implanted to last subject completing his/her last follow-up exam) is estimated to be seven years.

5.4 Analysis Execution

The study endpoints are descriptive without formal statistical hypotheses. An initial analysis is anticipated when 50 to 75 subjects have completed the 6 month follow up exam. The analysis will be descriptive and no formal interim analyses are planned for the purpose of early stopping or sample size re-estimation. Additional analyses are planned when all 75 implanted subjects have completed his/her 6 month follow-up. Additional analyses may be performed following completion of annual follow-up. A final report will be prepared once all implanted subjects have completed his/her five-year follow-up and all data collection has ended.

6. Determination of Sample Size

The study is descriptive and the sample size of 75 subjects was not determined by statistical sample size methods. However, a sample size of 75 subjects is adequate to achieve the study objectives and for an assessment of the procedural safety and efficacy of the study device in the study populations.

7. Statistical Methods

7.1 Study Subjects

7.1.1 Disposition of Subjects

Subject disposition will be illustrated in a flow diagram. Subject visits will be tabulated and compliance to the visit schedule and visit windows will be summarized, and attrition will be identified and summarized. Tabulations will include the number of subjects enrolled, attempted implant, implanted, died, withdrawn, lost-to-follow-up, and completed the scheduled follow-up visit for each visit.

7.1.2 Clinical Investigation Plan (CIP) Deviations

Deviations will be reported to Medtronic regardless of whether medically justifiable, pre-approved by Medtronic, or taken to protect the subject in an emergency. Study deviations will be reported on the Study Deviation CRF. Deviations will be reported by deviation category and visit. For each category, both protocol deviation and subject counts will be reported. Percentages will be based on subject counts and the denominator will include all subjects eligible for the visit, where applicable.

7.1.3 Analysis Sets

The enrolled population will consist of all subjects who signed the informed consent. The following analysis sets are defined within the enrolled population:

1. **Attempted Implant set:** The attempted implant data set will include all subjects with an attempted implant procedure, where an attempted implant is defined as when the subject is brought into the procedure room and any of the following have occurred: anesthesia administered, vascular line placed, Transesophageal echocardiography (TEE) placed or any monitoring line placed. Day 0 is the date of first attempted procedure.
2. **Implanted set:** The implanted data set includes all subjects with an attempted implant where the study device is implanted, defined as when the transcatheter aortic valve (TAV) is fully released from the delivery catheter system (DCS). Day 0 is the date of first attempted procedure.

In general, the primary analysis of safety, clinical outcomes, and quality of life (QoL) outcomes will be performed using the Attempted Implant analysis set and primary analysis of echo-related outcomes will be performed using the Implanted analysis set. The primary analysis population for each endpoint are detailed in Section 7.9. Analysis performed using analysis sets other than the primary would be considered supportive.

7.2 General Methodology

Continuous variables will be summarized descriptively with number of observations, mean, standard deviations, median, first and third quartiles, minimums and maximums. Categorical data will be presented as counts and percentages.

For time-to-event outcomes using Kaplan-Meier methods, the time points of 30 days, 6 months, 1 year, 2 years, 3 years, 4 years, and 5 years will correspond to 30, 183, 365, 730, 1095, 1460, and 1825 days post-implant, respectively. For each applicable time point, the event or event-free rate, the number of subjects at risk, the number of subjects with an event, the Greenwood standard error of the estimate, and the log-log transformed 95% confidence interval using the Greenwood standard error will be reported. For subjects with an event, the date of event will be based on the first event occurrence. For subjects without an event, date of censoring will be based on the latest of all follow-up visits, assessments, and events (for non-death events).

All statistical analyses will be performed using SAS version 9.4 or higher (SAS Institute, Cary, North Carolina, USA) or other widely accepted statistical or graphical software.

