Discharge	At the time of discharge from index TAVR procedure (at least 12 hours post-procedure) or within 7 days post implant, whichever comes first
30 Days	Between 30 and 45 days post implant
6 Months	Between 183 and 210 days post implant
1 Year	Between 365 and 395 days post implant
2 Years	Between 730 and 760 days post-implant
3 Years	Between 1095 to 1125 post-implant
4 Years	Between 1460 to 1490 days post-implant
5 Years	Between 1825 to 1855 days post-implant

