 - Invasive diagnostic evidence with right heart catheterization showing a pulmonary capillary wedge pressure (pulmonary artery occlusion pressure) \geq 18 mmHg, central venous pressure \geq 12 mmHg, or a cardiac index < 2.2 L/min/m²
- 4) The patient receives at least one of the following treatments specifically for HF:
 - Initiation of intravenous diuretic or vasoactive agent (e.g. inotrope, vasopressor, or vasodilator)
Note that signification augmentation of oral diuretic therapy will not be sufficient to fulfill the urgent HF visit criteria
 - Mechanical or surgical intervention, including:
 - Mechanical circulatory support (e.g. intra-aortic balloon pump, ventricular assist device, extracorporeal membrane oxygenation, total artificial heart)
 - Mechanical fluid removal (e.g. ultrafiltration, hemofiltration, dialysis)

*Note that clinic visits for scheduled administration of HF therapies or procedures (e.g. intravenous diuretics, intravenous vasoactive agents, or mechanical fluid removal) **do not** qualify as non-hospitalized HF events.*

Device Success⁶³

All of the following:

- Absence of procedural mortality, **AND**
- Correct positioning of a single prosthetic heart valve into the proper anatomical location, **AND**
- Absence of patient prosthesis-mismatch and mean aortic valve gradient < 20 mmHg (or peak velocity < 3 m/sec), **AND**
- Absence of moderate or severe prosthetic valve regurgitation.

Bioprosthetic Valve Dysfunction (BVD)⁶³: Any of the following

- **Stenosis: moderate/severe**; any of the following:
 - Peak aortic velocity > 4 m/s OR mean aortic gradient > 40 mmHg, AND EOA < 0.8 cm²
 - Peak aortic velocity > 4 m/s OR mean aortic gradient > 40 mmHg, AND EOA ≥ 0.8 cm², **AND** DVI < 0.25
 - Peak aortic velocity ≤ 4 m/s and mean aortic gradient ≤ 40 mmHg, AND EOA < 0.8 cm², **AND** DVI < 0.25
- **Paravalvular regurgitation: moderate**
- **Paravalvular regurgitation: severe**
- **Transvalvular regurgitation: moderate**
- **Transvalvular regurgitation: severe**
- **Total regurgitation: moderate**
- **Total regurgitation: severe**

Notes:

1. For subjects with BSA < 1.6 m², the EOA criteria for significant (moderate or severe) stenosis is < 0.6 cm²
2. For subjects with LVOT diameter > 2.5 cm, the DVI criteria for significant (moderate or severe) stenosis is < 0.2
3. Reporting of prosthetic valve dysfunction will be based on core lab results.

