 - Peak aortic velocity ≤ 4 m/s and mean aortic gradient ≤ 40 mmHg, AND EOA < 0.8 cm², AND DVI < 0.25

Note: In the above, for subjects with BSA < 1.6 m², the EOA criteria for significant (moderate or severe) stenosis is < 0.6 cm². Additionally, for subjects with LVOT diameter > 2.5 cm, the DVI criteria for significant (moderate or severe) stenosis is < 0.2.

- Moderate or severe paravalvular regurgitation
- Moderate or severe transvalvular regurgitation
- Moderate or severe total regurgitation

Analysis of BVD will be based on data collected on the core lab CRF. The numerator for each time point will include the number of subjects meeting any of the components of BVD. The denominator will include any subject with BVD and subjects with no evidence of BVD having evaluable data for all 4 components. BVD will be summarized with frequency counts and percentages. The components of BVD will also be summarized. The analysis will be performed using the Implanted set.

Additional Outcome Measure 12 - Bioprosthetic valve failure (BVF)⁽²⁾ at 30 days, 6 months, 1 year

Bioprosthetic valve failure (BVF) is defined as meeting any of the following:

- Autopsy findings of bioprosthetic valve dysfunction, likely related to the cause of death, or valve-related death (i.e. any death caused by bioprosthetic valve dysfunction or sudden unexplained death following diagnosis of bioprosthetic valve dysfunction)
- Repeat intervention (i.e. valve-in-valve TAVI, paravalvular leak closure or SAVR following confirmed diagnosis of bioprosthetic valve dysfunction)
- Severe bioprosthetic valve dysfunction

A Kaplan-Meier analysis as described in Section 7.2 will be performed for BVF at 30 days, 6 months, and annually through 5 years. The analysis will use the Implanted set.

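### Kaplan-Meier rates are read on the first day of each visit window, so silent severe valve dysfunction first seen at the 5-year echo after day 1825 enters no planned BVF rate

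*SAP*

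**What the plan says.** SAP 7.2 fixes the days on which every Kaplan-Meier curve is read: the time points "will correspond to 30, 183, 365, 730, 1095, 1460, and 1825 days post-implant, respectively". On dating, "For subjects with an event, the date of event will be based on the first event occurrence". On censoring, "For subjects without an event, date of censoring will be based on the latest of all follow-up visits, assessments, and events".

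The visit windows in Protocol 6.6 open on those same days and run forward only. The 6-month visit is "Between 183 and 210 days post implant" and the 5-year visit, the last one, is "Between 1825 to 1855 days post-implant".

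SAP 7.9.3 applies this to BVF: "A Kaplan-Meier analysis as described in Section 7.2 will be performed for BVF at 30 days, 6 months, and annually through 5 years". Severe BVD is by itself sufficient for BVF. For BVD, Protocol 13.8.3 note 3 says "Reporting of prosthetic valve dysfunction will be based on core lab results", and note 4 keeps BVD out of adverse-event reporting unless there are clinical sequelae. BVD has its own analysis in SAP 7.9.3, a proportion at each visit rather than a Kaplan-Meier rate: "The numerator for each time point will include the number of subjects meeting any of the components of BVD".

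The SAP mentions visit windows only for the compliance summary in 7.1.1.

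**The concern.** Reading a Kaplan-Meier curve on a fixed day is sound for events with a clinical date, such as death, stroke, hospitalization, pacemaker implantation or reintervention. Those are not affected. The difficulty is confined to outcomes that come to light only at a scheduled test.

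Silent severe BVD is the clear case. It has no adverse-event onset date, so the echo date is the only date the documents supply. Since each readout is the first day of the window, an on-schedule echo almost always falls after its own readout. At earlier visits this delays the event to the next readout. At 5 years the event is lost from BVF, while the same echo counts in the 5-year BVD percentage.

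Objective 2 (Protocol 4.1) is to estimate event rates for planning pivotal studies, and a 5-year BVF rate computed this way is biased downward.

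Some other outcomes are affected only if the test date is taken as the date of first occurrence: sub-clinical thrombosis, and conduction delay or atrial fibrillation first seen on a scheduled ECG. The adverse-event form also records onset, the CEC adjudicates these outcomes, and thrombosis may need imaging beyond the scheduled echo. If the test date were used, findings at the 6-month ECG would be missing from the 6-month safety rate. Those reported as adverse events would still appear in the SAP 7.10 tables at 1 year and in the listing.

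**Working it through.** The plan states no figure to reproduce, and the 75 subjects were not statistically determined. Event counts, onset rates and visit timing below are assumptions.

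**1. Readout days against windows** (SAP 7.2; Protocol 6.6)

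| Visit | Readout day | Window | Window days after the readout | Next readout |
|---|---|---|---|---|
| 30 days | 30 | 30–45 | 15 of 16 | 183 |
| 6 months | 183 | 183–210 | 27 of 28 | 365 |
| 1 year | 365 | 365–395 | 30 of 31 | 730 |
| 2 years | 730 | 730–760 | 30 of 31 | 1095 |
| 3 years | 1095 | 1095–1125 | 30 of 31 | 1460 |
| 4 years | 1460 | 1460–1490 | 30 of 31 | 1825 |
| 5 years | 1825 | 1825–1855 | 30 of 31 | none |

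All seven readouts are the first window day. A 4-year echo on day 1475 enters the 5-year rate; a 5-year echo on day 1840 enters none.

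**2. Findings first made at the 5-year echo.** Let k of n subjects have such a finding and let P be the share of visits on day 1825. The average planned contribution is k/n × P, and the chance that none is counted is (1 − P)^k. Even visits give P = 1/31.

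| k/n | Nominal-day rate | P = 1/31 | P = 0.25 | P = 0.50 |
|---|---|---|---|---|
| 1/75 | 1.3% | 0.04% | 0.33% | 0.67% |
| 3/75 | 4.0% | 0.13% | 1.0% | 2.0% |
| 3/60 | 5.0% | 0.16% | 1.25% | 2.5% |

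For k = 3 the chance that none is counted is (30/31)³ = 91%, 0.75³ = 42% and 0.5³ = 12.5%. Simulated Kaplan-Meier estimates, with event-free subjects censored at their own visit, agree with these averages.

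**3. Whole-course illustration: constant silent onset of 1% per year, no deaths or dropout.** The true 5-year rate is 1 − exp(−0.01 × 1825/365.25) = 4.87%. With even visits and no unscheduled echoes, the day-1825 readout captures onsets before the 4-year echo (mean day 1475), plus 1/31 of the remainder: 1 − exp(−0.01 × 1475/365.25) = 3.96%, and 3.96% + (4.87% − 3.96%)/31 = 3.99%.

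At the favorable end, half of visits fall on the first window day and there are 0.3 unscheduled echoes per year. Simulation then gives 4.5%. The ranges are:

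- 5 years: 4.0–4.5% against 4.9% true
- 1 year: 0.55–0.77% against 0.99%
- 6 months: about 0.1–0.3% against 0.50%

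The 5-year shortfall is (4.87% − 4.5%) × 75 = 0.3 to (4.87% − 3.99%) × 75 = 0.7 subjects. At 0.5% per year the 5-year rate is 2.0–2.3% against 2.5%; at 2% per year it is 7.8–8.8% against 9.5%.

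**4. Sampling error.** The exact 95% interval for 3/75 is 0.8% to 11.2%.

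**5. Reading at window close instead.** Because subjects are censored at their own visit, few remain at risk by day 1855. In simulation with even visits, 1, 2 or 3 events in 75 average 5.2%, 10.3% and 15.1%, against 1.3%, 2.7% and 4.0%.

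**The case against.** The strongest reply is that the loss depends on a dating rule the SAP does not state. It speaks of first occurrence, names no date source for BVF, and Protocol 7.7 lets the CEC use core-lab data. This is true, but for a silent finding the documents offer no date other than that of the echo.

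Second, the BVD definition pools moderate and severe stenosis, and only regurgitation has a separate severe grade. The clearly affected class is therefore silent severe regurgitation. That narrows the point but is enough to produce the loss.

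Third, 3 of 75 is a high count. Onset at 0.5–2% per year implies roughly 0.4–1.4 subjects first detected at the 5-year echo, so the 1-of-75 row and the shortfall of 0.3–0.7 subjects are the more realistic guides. And if half of visits fall on day 1825, half of the findings are counted.

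Fourth, BVD and BVF would differ even with perfect dating, because one is a per-visit proportion pooling moderate and severe grades and the other is cumulative and includes valve-related death and reintervention. A difference between them is therefore not in itself proof of error.

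Finally, the key endpoints are at 30 days and 6 months, and before year 5 the effect on BVF is delay rather than loss. These points limit the importance. They do not supply the missing rule.

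**Conclusion.** The concern holds. Followed as written, SAP 7.2 puts silent severe BVD first seen on days 1826–1855 into no planned BVF rate, and moves such findings at earlier visits to the following readout. This rests on the echo date being the event date. An echo on day 1825 exactly, or an earlier unscheduled one, would be counted.

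The bias is downward. At an assumed onset of 1% per year it is about 0.4 to 0.9 percentage points at 5 years, well inside sampling error. It is a minor point: the study is descriptive, BVF is not a key endpoint, and the echo data still appear in the BVD and hemodynamic summaries.

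**What to change.** Add to SAP 7.2:

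- For BVF, and for any other Kaplan-Meier outcome whose only available date is that of an in-window scheduled echo or ECG, the event is assigned to that visit's nominal day (30, 183, 365, 730, 1095, 1460 or 1825).
- A documented onset or clinical date is used whenever there is one, and findings at unscheduled echoes keep the date of that echo.

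The censoring rule can stay. Event-free subjects seen in-window already remain at risk through the nominal day, because the window opens on it. The readout should not be moved to window close, for the reason in step 5.

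The cost is two or three sentences and a few lines of code, with no new data. Onsets between the nominal day and the visit are counted slightly early: at 1% per year, 4.91% against 4.87% true at 5 years. The rule covers in-window visits only, so a 5-year echo done after day 1855 would still be uncounted, as would an unscheduled echo after day 1825.

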10.3 Interim Analysis

An initial analysis is planned when the first 50 implanted subjects have completed his/her six-month follow-up; however initial analyses may be performed earlier if enrollment is slower than expected. Initial analyses will assess all safety and efficacy endpoints based on available data.

There are no formal interim analyses planned for purposes of “early-win” assessment, futility, or sample size confirmation.

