7.8 Interim Analyses

An initial analysis is planned when the first 50 to 75 implanted subjects have completed his/her 6 month follow-up; however initial analyses may be performed earlier if enrollment is slower than expected. Initial analyses will assess all safety and efficacy endpoints based on available data. The analysis will be descriptive and no formal interim analyses are planned for the purpose of early stopping or sample size re-estimation.

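### If the initial analysis runs before all subjects reach 6 months and includes the later ones, the SAP's censoring rule biases its 6-month Kaplan-Meier rates upward

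*SAP*

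**What the plan says.** - **Event date.** SAP 7.2: "For subjects with an event, the date of event will be based on the first event occurrence". Nothing requires the event to fall on or before the subject's last contact.
- **Censoring date.** SAP 7.2: "For subjects without an event, date of censoring will be based on the latest of all follow-up visits, assessments, and events". A parenthesis limits the last item to non-death events. No common data cut-off is named, and no status check at a cut-off is required.
- **Reading days.** The 30-day to 5-year time points "will correspond to 30, 183, 365, 730, 1095, 1460, and 1825 days post-implant, respectively", so the 6-month rate is read at day 183.
- **Trigger.** Protocol 10.3: "An initial analysis is planned when the first 50 implanted subjects have completed his/her six-month follow-up". SAP 5.4: "An initial analysis is anticipated when 50 to 75 subjects have completed the 6 month follow up exam". SAP 7.8: "An initial analysis is planned when the first 50 to 75 implanted subjects have completed his/her 6 month follow-up". The same SAP section lets the analysis be brought forward when accrual lags. Protocol section 5 also gives the range 50 to 75.
- **Data used.** SAP 7.8: "Initial analyses will assess all safety and efficacy endpoints based on available data". Safety, hospitalization and heart failure endpoints use the Attempted Implant set (SAP 7.9.1, 7.9.2.2, 7.9.2.3).
- **Visits.** Protocol 6.6 places the 30-day visit at days 30-45 and the 6-month visit at days 183-210, with none between.
- **Dropouts.** SAP 7.4 censors them at discontinuation. It does not address subjects still in follow-up.

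**The concern.** Kaplan-Meier estimation needs the end of observation to be unrelated to the outcome. Take a subject 150 days past implant at the time of analysis. If event-free, the subject leaves the risk set at about day 30-45 unless there was some other contact. With a stroke on day 100, the same subject counts as an event on day 100. Follow-up beyond the 30-day visit is therefore credited mainly to subjects who have something to report. Events enter the numerator while comparable event-free time is missing from the risk set, so the estimate moves up. The Greenwood interval does not reflect this.

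Estimating event rates for pivotal studies is the second primary objective (protocol 4.1), and protocol 5.2 names pivotal sample size estimation as a use of the data. Rates that are too high would make an event-driven pivotal design too small.

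**Working it through.** The documents give no event rate or Kaplan-Meier figure to reproduce, and the 75 subjects are stated not to come from a sample-size calculation. Event rates, event timing, uniform accrual and reporting lags below are assumptions.

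**Hand example.** 75 subjects are implanted. 50 have completed 6 months, and 25 are later subjects last seen at about day 37. After day 45 there is one event among the later subjects (day 80) and two among the completers (days 100 and 150).

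- SAP rule: the risk set is the 50 completers plus the one later subject with an event. Numbers at risk are 51, 50, 49. Rate = 1 − (50/51)(49/50)(48/49) = 3/51 = 5.9%.
- Same data with event-free subjects censored at the data cut, later subjects' follow-up spread over days 104-195: numbers at risk are 75, 74 and about 61 (49 completers plus about 12 later subjects). Rate = 1 − (74/75)(73/74)(60/61) = 4.3%.

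**Simulation.** 75 subjects were implanted uniformly over 9 or 20 months, the ends of the stated enrollment range. Visits were at discharge, days 30-45 and days 183-210. The cut came when the stated number had completed the 6-month visit. Events were known at once, and only scheduled visits moved the censoring date. There were 3,000 runs per setting. Mean 6-month estimate under the SAP rule, in percent:

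| Trigger | Subjects short of the 6-month visit | True 5 (2 by day 30) | True 10 (5 by day 30) | True 20 (5 by day 30) | True 17 (15 by day 30) |
|---|---|---|---|---|---|
| 40 | 24-35 | 5.9-6.6 | 11.5-12.5 | 23.4-26.2 | 17.9-18.0 |
| 50 | 23-25 | 5.7-6.0 | 11.1-11.6 | 22.8-24.3 | 17.7 |
| 60 | 15 | 5.4-5.6 | 10.7-10.9 | 21.9-22.4 | 17.3 |
| 75 | 0 | 5.0-5.1 | 10.0-10.1 | 19.9-20.0 | 17.0-17.1 |

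At a trigger of 50, three rules were tried that treat both groups alike: censoring at the cut with status confirmed, ignoring events after the last visit, or using only subjects who had reached 6 months. They gave 4.9-5.0, 10.0-10.1, 19.9-20.1 and 17.0. The event process here was non-terminal, which matters for the second rule (see the fix). The 30-day rate moved by at most about 0.5 point. The SD of the 6-month estimate at a trigger of 50 was about 3 to 6 points.

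**Sensitivity to capture lag.** True rate 10%, trigger 50, accrual over 9-20 months, 20-50% of the 6-month hazard in the first 30 days:

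- no lag: 10.9-12.9%
- 30-day lag before an event reaches the analysis file: 10.4-12.0%
- 60-day lag: about 9.8-11.0%
- 30-day lag, with one other contact in half of the subjects: 10.4-11.3%

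**The case against.** - **Inclusion of later subjects is inferred.** No sentence says that subjects short of 6 months enter the 6-month rates. It follows from the available-data wording together with an analysis set of all attempted implants. This stands, so the point is conditional.
- **Events are not known at once.** Table 4 of the protocol governs site reporting from first knowledge. The endpoints use adjudicated events, which need source documents. This stands: a lag reduces the bias, and at about 60 days it may be gone.
- **Event-free subjects can be observed past the 30-day visit.** Other events, assessments and unscheduled visits move censoring later for non-death endpoints, and all adverse events are reportable to the 6-month visit (protocol 7.2). This stands and shrinks the bias. It does not remove it, because protocol 6.9 defines unscheduled contacts by a possible endpoint event.
- **The look is descriptive and temporary.** There is no decision rule, numbers at risk are reported, and a full analysis follows once all implanted subjects complete 6 months. This stands. No passage says that pivotal sizing will use the initial look.

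A reader might infer that the initial rates must be too high for every endpoint, by as much as a quarter. The documents do not support that. The trigger range includes 75, where the bias is nil; acute kidney injury is defined only to day 7; and pacemaker implantation is affected only to the extent that it occurs late, on which the documents give no figure. A reader might also see the trigger as a protocol-versus-SAP conflict, but the protocol itself differs between section 5 and 10.3.

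**Conclusion.** The point holds conditionally. Given a trigger of 50 or earlier, and later subjects included, SAP 7.2 makes length of observation depend on outcome, and nothing in either document corrects this. The direction is upward for events reported between visits: death, stroke, hospitalization, heart failure events, and late reintervention or pacemaker.

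At an assumed true rate of 10% and a trigger of 50, the excess is about 0.4 to 2.9 points for lags of 0 to 30 days. The upper end needs immediate capture, fast accrual and mostly late events. The excess is below the sampling SD of about 4 points, negligible for periprocedural endpoints, and zero at a trigger of 75 and in the planned all-subject 6-month analysis. It is worth correcting because it runs in one direction, bears on a primary objective, and costs only wording.

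**What to change.** In SAP 7.2 and 7.8:

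1. Set a data cut-off date for each analysis and apply one observation rule to all subjects.
2. For each time point, include every Attempted Implant subject whose procedure date is early enough that the visit window closed on or before the cut-off (day 210 for 6 months), whatever the subject's status. Later subjects contribute only to time points whose window has closed.
3. Time the initial analysis so that at least the first 50 implanted subjects meet this condition. Selecting by procedure date keeps subjects who were attempted but not implanted, as the analysis set requires.
4. State one trigger in protocol section 5, protocol 10.3, SAP 5.4 and SAP 7.8.

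Counting events only up to the last completed scheduled contact may look equivalent but should not be adopted. A subject who dies attends no later visit, so that rule would exclude deaths.

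Cost: up to about 25 partly followed subjects leave the initial 6-month rates, and the analysis may wait briefly for windows to close. Precision is essentially unchanged: at a 10% rate the simulated SD is about 4.2-4.6 points, against 4.1-4.5 under the present rule.
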